## Protocol Summary

Full Title:	A Phase 2 Randomized, Double-Blind, Placebo-Controlled Study to Evaluate the Safety and Efficacy of Subcutaneous (sc) Benralizumab in Reducing Eosinophilia in Subjects with Hypereosinophilic syndrome (HES)
Short Title:	Benralizumab for treatment-refractory HES
Clinical Phase:	2
IND Sponsor:	OCRPRO/NIAID/NIH
Conducted by:	NIAID/LPD
Principal Investigator:	[name]
Sample Size:	N=20
Accrual Ceiling:	N=25
Study Population:	Adult subjects aged 18-75 with PDGFRA -negative HES who are symptomatic with AEC >1000/ $\mu$ L on stable HES therapy for at least 1 month
Accrual Period:	2 years
Study Design:	This will be a randomized, placebo-controlled, double-blind study followed by an open-label extension. A maximum of 20 subjects will be randomized (1:1) to receive sc injections of 30 mg of benralizumab or placebo at 0, 4 and 8 weeks. Eosinophil counts for a subject will be blinded and background HES therapy will not be tapered until that subject has reached 13 weeks on study. Beginning at the 12 week visit, all subjects will receive open-label benralizumab (30 mg sc) every 4 weeks for 3 doses. Subjects with an AEC<1000/ $\mu$ L and improvement in clinical symptoms without an increase in background HES therapy (responders) at the 24 week visit will continue to receive benralizumab every 4 weeks for the duration of the study (1 year). Non-responders will not receive additional doses of benralizumab. Following the initial dose of benralizumab or placebo and the first open-label (at 12 weeks) dose of benralizumab, subjects will be followed daily for 3 days, weekly for 4 weeks, and every 2 weeks for 8 weeks. Subsequent visits will be at 4 weeks intervals for responders and at 12 week intervals for non-responders for the duration of the study. For subjects who complete the study and for whom benralizumab provides sustained clinical benefit, drug may be provided on an open-label extension. After 2 years of stable and complete response to benralizumab, the dosing interval may be increased to every 8 weeks. Subjects will receive diphtheria-

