## 3 Study Design

### 3.1 Description of the Study Design

This study will be a single center trial with 5 parts: 1) randomized, double-blind sc benralizumab vs. placebo every 4 weeks for 12 weeks, 2) open-label sc benralizumab every 4 weeks for 12-36 weeks, 3) open-label sc benralizumab extension for benralizumab responders, with doses every 4 weeks for 6 months, 4) open label substudy of sc benralizumab administration every 8 weeks in complete responders, and 5) open-label extension of self-administered sc benralizumab using an autoinjector for subjects with a sustained and complete response, for a minimum of 2 years. Eligible subjects enrolled on study protocol 94-I-0079 (Activation and function of eosinophils in conditions with blood or tissue eosinophilia) or referred from outside physicians for evaluation of hypereosinophilia will be invited to participate. A maximum of 20 subjects will be enrolled.

Baseline evaluation will include a complete history and physical examination, routine laboratory testing and assessment of end organ involvement (see [Appendix A](#)). Baseline research studies will include bone marrow aspirate and biopsy to assess eosinophil and mast cell numbers and activation, storage of peripheral blood mononuclear cells (PBMC) for future studies, assessment of baseline eosinophil activation and T/B/NK subsets by flow cytometry, and measurement of serum markers of eosinophil and mast cell activation. Potential predictors of response to benralizumab, including eosinophil surface and soluble IL-5R $\alpha$  levels and plasma cytokine profiles, will also be explored.

Part 1: Benralizumab (30 mg) or placebo will be administered sc every 4 weeks for 3 doses (at weeks 0, 4 and 8). Eosinophil counts will be blinded during this time and background HES therapy will not be tapered.

Part 2: Following the placebo-controlled portion of the trial, all subjects will receive an sc injection of benralizumab at weeks 12, 16, and 20. Eosinophil counts will be unblinded after the first week of open-label therapy (study week 13) and HES therapy may be tapered if clinically indicated. Subjects demonstrating a response at the 24 week visit (eosinophil count <1000/ $\mu$ L and stable or improved clinical symptoms without an increase in background HES therapy) will receive additional 30 mg sc injections every 4 weeks for 6 doses. Non-responders will receive no further doses of benralizumab.

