Appendix F: FASENRA PEN: Instructions for Use).

### **5.3.2 Study Drug Dosing**

Population modelling of clinical efficacy endpoints (Asthma Exacerbation Rate (AER), Asthma Control Questionnaire (ACQ), and Forced Expiratory Volume in 1 second (FEV1)) from the interim analysis for the Phase 2 asthma study, MI-CP220, and stochastic simulations identified the optimal dose and regimen for the pivotal Phase 3 studies with benralizumab in adult subjects with asthma as 30 mg every 4 weeks for 3 doses then every 8 weeks thereafter. This dosing regimen corresponds to the ED90 for AER and ACQ, and maintains a steady-state PK exposure close to EC90 levels for FEV1 and ACQ. With a steady-state PK exposure 50% higher than 20 mg every 8 weeks, the 30 mg dose every 8 weeks is expected to reduce the impact of PK variability related to factors such as higher body weight. The incidence of ADA (especially high-titer ADA) and the impact on PKPD were dose-dependent with decreased incidence and impact at higher doses. However, the ADA response was not more frequent in those subjects with blood eosinophils  $\geq 300$  cells/ $\mu$ L (20.7%) as compared to those with blood eosinophils  $< 300$  cells/ $\mu$ L (21.7%). Since doses higher than 20 mg are expected to reduce the impact of ADA without modifying the dose interval, and there are no identified safety risks that would warrant consideration of a lower dose, subjects will receive 30 mg every 4 weeks for 3-12 doses depending on whether they receive drug or placebo during the first part of the study and whether they demonstrate a clinical and hematologic response at study week 24.

Subjects who complete the study and for whom benralizumab appears to provide a sustained clinical benefit, may be eligible to receive drug under an open-label extension until regulatory approval and commercial availability of the marketed drug to prescribing physicians (for HES), or until AstraZeneca ceases development of benralizumab for this indication. Complete responders may be eligible to extend the dosing interval to every 8 weeks after sustained and complete remission of eosinophilia for  $\geq 2$  years at the investigator's discretion.

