Due to the limited sampling schedule, the PK assessment will be primarily based on the observed steady-state serum trough (predose) concentrations,  $C_{trough}$ . Empirical evaluation of potential impact of demographic covariates and ADA on  $C_{trough}$  will be conducted. Serum concentrations of benralizumab, summary statistics, empirical covariate analysis results and PK profiles will be provided in a clinical PK report (an addendum to the CSR).

To further characterize the pharmacokinetic properties of benralizumab in HES, the PK data will be merged with those from other clinical studies for a population-based, which will be presented in a separate pharmacometrics report outside of the CSR.

- **Calculation or derivation of immunogenicity variables**

ADA assessments will be conducted utilizing a tiered approach (screen, confirm, titer). Evaluations will be made at baseline (prior to benralizumab administration), and at specified time points during the treatment and follow up phases of the study or discontinuation. ADA titers by treatment group and visit will be summarized. The association of ADA status (positive or negative) with treatment-emergent adverse events (TEAEs)/ treatment-emergent serious adverse events (TESAEs), benralizumab concentration and blood eosinophil levels will be evaluated. In addition, the association of ADA titers ( $\geq$ median titer vs.  $<$  median titer) with TEAEs/ TESAEs, benralizumab concentration and blood eosinophil levels will be evaluated for ADA positive subjects only.

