- 5) Mechanism of post-treatment reactions
- Post-injection reactions have been observed in some, but not all, subjects 4-6 hours following the first dose of benralizumab vs. placebo or the first dose of open-label benralizumab. These reactions have been characterized by fever, nausea, fatigue and myalgias and a rise in LDH. Reactions have not been observed following injections at other study time points and the severity of the reaction does not appear to be related to pre-treatment eosinophil count. Similar reactions have not been described in studies of benralizumab in subjects with asthma, but were seen in some subjects in phase i dose finding studies.
  - Potential mechanisms for these reactions include 1) NK activation and cytokine release and/or 2) eosinophil lysis. In order to begin to examine these possibilities, whole blood flow will be performed to assess markers of activation and degranulation of NK cells (CD63 and CD107a) and eosinophils (CD69 and CD63) prior to and at 3-6 hours post the study drug injection at week 0 and week 12. Plasma levels of cytokines, granule proteins and other inflammatory markers will also be assessed.

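### The ADA titer analysis splits ADA-positive subjects at the median; with about 4 positives expected if the asthma ADA rate carries over, a rank analysis of the same data would be more informative

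*Combined protocol and SAP*

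**What the plan says.** The immunogenicity paragraph of Section 13.3 plans several pieces of work. ADA titers are summarised by treatment group and visit. "The association of ADA status (positive or negative) with treatment-emergent adverse events", drug concentration and eosinophil level is examined in all subjects. As an addition, titer is cut at its median and the two halves are compared on TEAEs and serious TEAEs, while "benralizumab concentration and blood eosinophil levels will be evaluated for ADA positive subjects only". The PK paragraph of the same section also provides for an empirical look at the effect of ADA on trough concentration.

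For the median split, Section 13.3 gives no test, no minimum number of ADA-positive subjects, no fallback if there are few, and no rule for which titer (peak, last or per visit) defines the median. Section 13.4 sets a two-sided 5% level for all tests.

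The Protocol Summary fixes the size: "A maximum of 20 subjects will be randomized (1:1) to receive sc injections of 30 mg of benralizumab or placebo". Section 3.1 adds that "all subjects will receive an sc injection of benralizumab at weeks 12, 16, and 20", so all 20 can contribute on-drug ADA data, but only about 10 of them during the blinded part. The only ADA rates are in Section 5.3.2, where the asthma data are described: "the ADA response was not more frequent in those subjects with blood eosinophils" of 300 or more per microlitre (20.7%) than below 300 (21.7%).

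**The concern.** A median split uses only which half a titer falls in. With a handful of positive subjects that loses most of the information, and the cut is set by the data, so it need not separate high titers from low ones. Section 5.3.2 singles out high-titer ADA as the form whose incidence and impact depended on dose, and Section 1.1.2 links high titers to reduced exposure in monkeys, so the titer scale is the part of interest.

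PK and ADA are a secondary objective (Section 2.2, item 5) and a secondary endpoint. If the split is formally tested on about four subjects, a non-significant result is almost certain whatever the truth, and a report could take it as evidence that titer does not matter.

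**Working it through.** **Plan's own figures.** The documents give no sample size or power for the ADA analysis. Table 2, for the primary endpoint, reproduces by exact enumeration with a one-sided Fisher test at 2.5%: 10 per group, 60% v 1% responders, gives 78.97% against the stated 79.0%, and all 15 cells agree within 0.1 point. This confirms the testing convention used below.

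**Inputs.** 20 treated subjects (Protocol Summary, Section 3.1). Two-sided 5% level (Section 13.4). Two-group tests named elsewhere in Section 13.3: Wilcoxon-Mann-Whitney for continuous outcomes and central Fisher for binary ones. ADA rate about 21% (Section 5.3.2), taken here as an assumption and varied.

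**Step 1, expected positives.** 20 × 0.21 = 4.2, so about 2 v 2 after a median split.

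**Step 2, smallest attainable p.** For x positives split into groups of k and x − k, complete separation gives a two-sided p of 2/C(x, k), the same for both tests. For a rank correlation within the positives, perfect ordering without ties gives 2/x!.

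| Positives | Split | Median split, 2/C(x, k) | Rank correlation, 2/x! |
|---|---|---|---|
| 4 | 2 v 2 | 2/6 = 0.333 | 2/24 = 0.083 |
| 5 | 2 v 3 | 2/10 = 0.200 | 2/120 = 0.017 |
| 6 | 3 v 3 | 2/20 = 0.100 | 2/720 = 0.003 |
| 7 | 3 v 4 | 2/35 = 0.057 | below 0.001 |
| 8 | 4 v 4 | 2/70 = 0.029 | below 0.001 |

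The split needs at least 8 positives to reach 5%; the rank analysis needs at least 5.

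**Step 3, how often that many occur.** With the number of positives X taken as Binomial(20, rate):

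| Assumed ADA rate | P(X ≤ 7): split cannot reach 5% | P(X ≥ 8): split can | P(X ≥ 5): rank analysis can |
|---|---|---|---|
| 15% | 99.4% | 0.6% | 17.0% |
| 20.7% | 96.1% | 3.9% | 40.1% |
| 21% | 95.8% | 4.2% | 41.4% |
| 21.7% | 95.0% | 5.0% | 44.5% |
| 25% | 89.8% | 10.2% | 58.5% |
| 30% | 77.2% | 22.8% | 76.2% |

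At 21% there is also a 5.7% chance of 0 or 1 positives, when no split exists. If only the 10 subjects on drug in the blinded part counted, P(X ≤ 7) would be 99.99%.

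**Step 4, limits of these figures.** Tied titers make the split unequal and raise its smallest p (8 subjects split 2 v 6: 2/28 = 0.071); they also raise the smallest p of the rank analysis. With 5 positives the rank analysis reaches 5% only if the ordering is perfect, so the last column shows where 5% is attainable, not power. With the minimum-likelihood Fisher test instead of the central version, 3 v 4 gives 1/35 = 0.029, 7 positives are enough, and 95.8% falls to 89.3%. The rank gain applies to continuous outcomes. For a yes/no adverse event with m events among x positives, ranking titer still gives at best 2/C(x, m), so it does not improve on the bound for the split.

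**The case against.** The strongest reply is that no test is planned. Section 13.3 says only that these associations will be evaluated, its safety data are summarised descriptively and listed by subject, and the 5% level in Section 13.4 governs tests that are run. This stands. A reader might infer that the plan commits to a test that cannot succeed; the documents do not support that. The 96% is conditional on the plan's exact or rank tests being carried over, and a t-test could fall below 0.05 even at 2 v 2.

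The 21% is also not a planning assumption for HES. It is asthma data, and Section 5.3.2 says that ADA incidence falls at higher doses. That stands too, and is why a range is shown. A lower rate strengthens the point; a 30% rate weakens it but leaves 77%.

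Nor does the plan discard the titer scale altogether. The by-visit titer summary, the trough evaluation and the ADA-status comparison remain. For the same reason, ranking titer across all 20 with negatives scored 0 adds less than it seems to. With 4 positives its smallest p is 2/(20!/16!) = 2/116,280, but most of that is the positive v negative contrast, where the planned 4 v 16 comparison already allows 2/C(20, 4) = 2/4,845 = 0.0004.

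A reader might further infer that the ADA-status analysis would credit ADA with reactions that preceded it, since "Post-injection reactions have been observed in some, but not all, subjects 4-6 hours following the first dose of benralizumab vs. placebo" while routine on-drug ADA sampling starts at week 4. The documents do not support this. Section 5.3.1 asks for an ADA sample during any acute reaction, baseline ADA is measured, and Section 13.3 is silent on time order rather than ignoring it. Counting only events on or after the first positive sample would also lose events between seroconversion and the next four-weekly sample.

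**Conclusion.** The point holds in a limited form. The median split is a weak way to use titer in a trial of this size, and a better one is available from the same samples. At an ADA rate near 21%, about 4 positives are expected and, under the plan's own exact tests, the split could not reach 5% in about 96% of trials; the range is 99% to 77% for rates of 15% to 30%. Analysing ranks within positives raises the share of trials in which 5% is attainable from about 4% to about 41% at 21%, before ties.

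This rests on three assumptions: exact or rank tests are used, the asthma rate is a fair guide, and all 20 subjects contribute. It concerns one supplementary secondary analysis and is a desirable improvement rather than a necessary one.

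**What to change.** In Section 13.3, replace the median split by an analysis of titer on its rank scale (exact Spearman or permutation) against trough concentration and AEC at the same visit, within ADA-positive subjects, and state which titer is used. Optionally add the same analysis across all benralizumab-treated subjects with negatives scored 0, noting that it largely repeats the planned ADA-status comparison. With fewer than 5 positives, label the result descriptive, list titer, trough, AEC and TEAEs by subject, and say that the data cannot support a conclusion of no association.

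The cost is a wording change, with no new samples or visits. The high v low titer table is lost, and the result remains imprecise under any method.

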### **13.4 Final Analysis Plan**

The primary endpoint is the number of subjects with a  $\geq 50\%$  change in AEC. The details of the statistical tests used for this endpoint is described in Section 13.3. For this test and all tests, we define significance using a two-sided 5% level or equivalently a one-sided 2.5% level. If the study shows that there is a significant reduction in AEC, this would merit further study of benralizumab in HES. This design relies on the assumption that the type of HES patients included in this study would not have 50% improvement in their eosinophil count in the absence of a change in therapy. This is a well-established assumption in the HES research community.

This single center trial has 2 parts: 1) a randomized, double-blind comparison of sc benralizumab vs. placebo every 4 weeks for 12 weeks, 2) an open-label extension of sc benralizumab every 4 weeks for 12-36 weeks. The primary endpoint and secondary and exploratory endpoints based on the data from the first part of the study will be analyzed once all 20 subjects have completed the 13 weeks visit and data is unblinded.

Since there are only 20 patients in the study, both an intent-to-treat and a per-protocol analysis may be done. For the intent-to-treat analysis, we will impute a “worst case” post-treatment AEC, whereby we will use the maximum of the baseline AEC or the last AEC as the post-treatment AEC for analysis. If a patient does not complete treatment, that patient may be removed from the per-protocol analysis.

Although we do not specify the exploratory analyses in advance, we do note that care will be taken in making inferences when many analyses are undertaken. If needed multiple comparison adjustments will be made.

## **14 Ethics/Protection of Human Subjects**

## **14.1 Informed Consent Process**

Informed consent is a process where information is presented to enable persons to voluntarily decide whether or not to participate as a research subject. It is an on-going conversation between the human research subject and the researchers which begins before consent is given and continues until the end of the subject's involvement in the research. Discussions about the research will provide essential information about the study and include: purpose, duration, experimental procedures, alternatives, risks and benefits. Subjects will be given the opportunity to ask questions and have them answered.

The subjects will sign the informed consent document prior to undergoing any research procedures. The subjects may withdraw consent at any time throughout the course of the trial. A copy of the informed consent document will be given to the subjects for their records. The researcher will document the signing of the consent form in the subject's medical record. The rights and welfare of the subjects will be protected by emphasizing to them that the quality of their medical care will not be adversely affected if they decline to participate in this study.

## **14.2 Subject Confidentiality**

All records will be kept confidential to the extent provided by federal, state and local law. The study monitors and other authorized representatives of the Sponsor may inspect all documents and records required to be maintained by the Investigator, including but not limited to, medical records. Records will be kept locked and all computer entry and networking programs will be done with coded numbers only. Clinical information will not be released without written permission of the subject, except as necessary for monitoring by IRB, the FDA, the NIAID, the OHRP, AstraZeneca or the sponsor's designee.

# **15 Data Handling and Record Keeping**

## **15.1 Data Capture and Management**

Study data will be maintained in CRIMSON and collected directly from subjects during study visits and telephone calls, or will be abstracted from subjects' medical records. Source documents include all recordings of observations or notations of clinical activities and all reports and records necessary to confirm the data abstracted for this study. Data entry into CRIMSON will be performed by authorized individuals. The Investigator is responsible for assuring that the data collected are complete, accurate, and recorded in a timely manner.

If a subject receives drug at an outside site on the long-term extension,(after week 48), the outside PI will provide documentation of drug administration, AE/SAEs and laboratory testing as required by the protocol. These will be entered into CRIMSON by the NIH study team.

## **15.2 Record Retention**

The investigator is responsible for retaining all essential documents listed in the ICH Good Clinical Practice Guideline. Study records will be maintained by the PI for a minimum of 3 years and in compliance with institutional, IRB, state, and federal medical records retention requirements, whichever is longest. All stored records will be kept confidential to the extent required by federal, state, and local law.

Should the investigator wish to assign the study records to another party and/or move them to another location, the investigator will provide written notification of such intent to OCRPRO/NIAID with the name of the person who will accept responsibility for the transferred records and/or their new location. Destruction or relocation of research records will not proceed without written permission from NIAID/OCRPRO.

## Appendix B: Schedule of Procedures/Evaluations

Events	Baseline	Placebo-controlled Phase								Open Label Phase												EXTENSION		
	Day 0 to -14	Day 0	Days 1,2,3	Wk 1,2,3	Wk 4	Wk 6	Wk 8	Wk 10	Wk 12	Days 85,86,87	Wk 13,14,15	Wk 16	Wk 18	Wk 20	Wk 22	Wk 24	Wk 28	Wk 32	Wk 36	Wk 40,44	Wk 48	Q 6 Mon ths	Q12 Mont hs	
	Window			± 2d	± 2d	± 3d	± 3d	± 3d	± 3d		± 2d	± 2d	± 3d	± 3d	± 3d	± 3d	± 4d	± 4d	± 4d	± 4d	± 4d	± 7d	± 7d	
Informed consent	X																							
Complete medical history and physical examination	X																							
Targeted medical history, including HES symptom questionnaire		X	X	X	X	X	X	X	X	X	X	X	X	X	X	X	X	X	X	X	X	X	X	X
Targeted physical examination		X	X	X	X	X	X	X	X	X	X	X	X	X	X	X	X	X	X	X	X	X	X	X
Vital signs, including weight	X	X 	X	X	X	X	X	X	X	X	X	X	X	X	X	X	X	X	X	X	X	X	X	X
Study Drug																								
Study Drug administration 		X			X		X		X			X		X		X 	X 	X 	X 	X 				
Study Procedures																								
Tdap vaccine																X 								
ECG (12-lead)	X								X							X			X		X		X	
Echocardiogram	X								X							X			X		X		X	
Pulmonary function tests	X								X							X			X		X		X	
Bone marrow aspirate and	X								X															

biopsy																							
Tissue biopsy of affected organs	X 								X 							X 			X 		X 		X 
Clinical and safety laboratory testing																							
Electrolyte Panel	X	X 	X	X	X	X	X	X	X	X	X	X	X	X	X	X	X	X	X	X	X	X	X
Hepatic Panel	X	X 	X	X	X	X	X	X	X	X	X	X	X	X	X	X	X	X	X	X	X	X	X
Mineral Panel	X	X 	X	X	X	X	X	X	X	X	X	X	X	X	X	X	X	X	X	X	X	X	X
CBC w/ differential	X	X 	X	X	X	X	X	X	X	X	X	X	X	X	X	X	X	X	X	X	X	X	X
PT/PTT	X								X														
ESR, CRP	X				X		X		X			X		X		X	X	X	X	X	X	X	X 
LDH, CPK	X	X	X	X	X	X	X	X	X	X	X	X	X	X	X	X	X	X	X	X	X	X	X
Total Protein	X				X				X			X		X		X	X	X	X	X	X	X	X 
Troponin	X								X							X			X		X		X 
Uric acid	X				x		x		X			x		x		X	x	x	X	x	X	x	X 
HbgA1c	X								X							X							
Urinalysis	X	X 	X	X	X	X	X	X	X	X	X	X	X	X	X	X	X	X	X	X	X	X	
Serum pregnancy test	X 	X 			X 		X 		X 			X 		X 		X 	X 	X 	X 	X 	X 	X 	X 
Serum B12 levels	X								X							X			X		X		X 
Serum tryptase levels	X	X 	X	X	X	X	X	X	X	X	X	X	X	X	X	X	X	X	X	X	X	X	
Serum immunoglobulin levels	X								X							X			X		X		X
Serum IgE levels	X								X							X			X		X		X
Tetanus Toxoid IgG Antibody									X 								X 						
Research laboratory studies																							

Eosinophil and PBMC purification from whole blood	X								X							X			X		X		X	
Serum, plasma and urine for eosinophil granule protein and mediator levels	X	X 	X	X	X	X	X	X	X	X	X	X	X	X	X	X	X	X	X	X	X	X	X	X 
Serum for PK studies and ADA measurement	X				X		X		X				X		X		X	X	X	X	X	X	X	X
Bone marrow flow cytometry	X								X															
T and B cell receptor rearrangement studies	X								X													X		X
IL-5 Receptor expression	X								X							X			X		X			
Whole Blood pre/post		X							X															
TBNK cell subsets									X							X			X		X			X
Study Assessments																								
Assessment of end organ involvement	X								X							X			X		X			X
Concomitant medication history	X	X 	X	X	X	X	X	X	X	X	X	X	X	X	X	X	X	X	X	X	X	X	X	X
Collection of adverse events		X 	X	X	X	X	X	X	X	X	X	X	X	X	X	X	X	X	X	X	X	X	X	X

